### **Recruitment:**

Recruitment to participants discharge will follow the following steps: .

- Patient sees ENT surgeon for standard of care visit to discuss upcoming (to be scheduled) tonsillectomy with or without adenoidectomy at which time, IRB-approved study flyers will be available to patients in the surgeons' exam rooms.
- The surgeon who is planning a patient's tonsillectomy with or without adenoidectomy gives the clinic Medical Support Assistant (MSA) a surgical scheduling form (STANDARD OF CARE)
- Approximately 30 days prior to surgery, the MSA schedules the patient's tonsillectomy with or without adenoidectomy if a time slot is available; if not, the MSA calls the patient within next 30 days when a slot is available. The MSA also schedules an appointment for the patient to see CRNA and RN (1-3 days pre surgery) (STANDARD OF CARE.) At this time the MSA gives the patient an OPTIONAL RESEARCH PACKET (Appendix G) in which there is the following:
  - ❖ Study Flyer (Appendix G)
  - ❖ Patient Information sheet (Appendix G)
- The MSA's will go by a specific script on what to say to potential candidates when giving them the OPTIONAL RESEARCH PACKET. (Appendix F) .
- 
- The PI, AI or any other designated team members will use the S3 list for potential participants that are scheduled for a tonsillectomy with or without adenoidectomy and will call them as previously approved for those that had no address. They will utilize the previously approved script that has been adjusted slightly for their role. (Appendix G1) The PI or AI will go over the consent at the PAU appointment or morning of surgery

IRBNet Number: 381600-19

PI: [name]

Protocol Title: **A randomized, single-blind, prospective trial of auricular acupuncture for the reduction of post-operative tonsillectomy pain in adults.**

Initial Date Submitted: 6/13/2013

Revision Date: 7/17/17

giving the potential participants ample time for questions or concerns.

- If a potential participant contacts the study team, a team member will arrange for the participant to review the consent at his or her pre-admission appointment. The study team will ask if the patient would like an emailed copy of the consent document. If yes, the team member will send her/him the consent form by email or postal mail to review. The study team member will not maintain the email or postal address on file.
- 
- If screening criteria based on inclusion and exclusion criteria are not met the potential participant will be thanked for their time and informed that they do not qualify for the study.
- If the patient meets the screening criteria and verbalizes interest in participating in the study, he or she is notified that s/he can be scheduled to further review and complete the consent paperwork if s/he wishes with study staff when s/he is present for the pre-admission appointment or at another time convenient for the potential participant. Then, at that time, the potential participant will have a chance to review any questions s/he may have about the study and complete the study consent paperwork if s/he wishes to participate. Consenting will take place in advance of the day of the procedure; if possible and if not a team member will meet with potential participant on the day of surgery in holding. Once a subject has consented to be in the study, the individual consenting them will interview them for demographics, medical history, medication history, and allergies (Appendix A). The pain diary will be reviewed at this time as well. If the subject is determined to be eligible for the study, her/his scheduled date of surgery will be confirmed. The PI will keep a list of all subjects and their respective surgery dates in a password protected electronic enrollment log kept in the V drive.
- **Home diary teaching:** At the Pre admit and/or consent appointment, a research team member will review the home pain diary with the subject. They will be asked to record their pain score in 6 hour intervals for 24 hours after hospital discharge and every 24 hours for a total of 10 days after the surgery. Subjects will not be asked to wake up at night to record pain level. Subjects will be asked to return their pain scores by phone, email, or mail (addressed envelope provided). If the subject has not sent their diary by day 15, an attempt at a reminder to the subject via phone call or email (whichever the subject prefers, as collected during enrollment) will be done. .
- **On the day of the surgery:** On the day of surgery, the randomization category will be determined by the PI or AI acupuncturists by opening the corresponding subject number envelope. Prior to surgery, the PI or AI acupuncturists will introduce him or herself to the subject (if not already done so) and confirm enrollment in the study. Anesthesia for the surgical case will then proceed per standard of care.

IRBNet Number: 381600-19

PI: [name]

Protocol Title: **A randomized, single-blind, prospective trial of auricular acupuncture for the reduction of post-operative tonsillectomy pain in adults.**

Initial Date Submitted: 6/13/2013

Revision Date: 7/17/17

After the patient has been fully anesthetized, and prior to the start of the tonsillectomy, the study PI or AI acupuncturists will place the acupuncture needles if randomized to the acupuncture group. Initiation of the surgical case will not be delayed for acupuncture needle placement. If the patient is randomized to the control group, no intervention will occur.

The procedure for the auricular acupuncture is standardized based on the Battlefield Acupuncture technique. The ear will be cleaned with alcohol prior to insertion of the needles. Five sterile, single-use, gold needles will be placed in each ear according to the figure below. The needles penetrate about a millimeter (or 4/100ths of an inch) into the skin.

Figure 1. Five points of Battlefield Acupuncture

At the end of the surgical case, prior to fully awakening the patient, the PI or his designee will remove the acupuncture needles.

Per standard of care, the providing anesthesiologist or PACU nurse will document in Essentris the subject's pain score every 15 minutes for one hour and then hourly until discharge from the PACU. A pain score will also be recorded in

IRBNet Number: 381600-19

PI: [name]

Protocol Title: **A randomized, single-blind, prospective trial of auricular acupuncture for the reduction of post-operative tonsillectomy pain in adults.**

Initial Date Submitted: 6/13/2013

Revision Date: 7/17/17

Essentris when prescribed as needed (PRN) pain medications are requested.

Anesthesia and pain medication will be provided per standard of care by the anesthesiologist assigned to the surgical case. All medications given will be documented in Essentris. All discharge instructions by the surgeon and anesthesiologist will be per standard of care.

PACU nurse education will be per standard of care only; the PACU nurse will not be responsible for any study education.

Data will be collected by the PI, AIs, on the day of surgery and recorded on the form found in Appendix B.

**Data collection:** Data will be collected and entered into three forms (Appendices A-C). All forms will be maintained in a locked file cabinet in the PI's locked office. Data will be collected during the initial subject interview by the individual consenting them (Appendix A), on the day of surgery by the PI (Appendix B), and from the home pain diary. (Appendix C). Data on the day of surgery may also be collected from Essentris or the anesthesia record once the patient has been discharged (as all data needed will be recorded in Essentris or the anesthesia record). Data will be transferred from these forms to an electronic Data base. Each patient will be allocated a study ID number, and thereafter will be referred to by that number in the database. An Excel spreadsheet with all current data will be where the data is to be entered by a research team member. It will be maintained in the V drive with limited password access. Only research team members will have access.

- Total doses of opioid analgesics in the preoperative, intraoperative and postoperative period will be converted to IV morphine equivalents by the PI or research staff member. They will use John Hopkins Opioid Program's conversion at <http://www.hopweb.org/hop/hop.cfm>
- **Acupuncture Competence:** The PI completed the 300 CME Helms Medical Acupuncture Course, the DOD wide approved acupuncture course.

• **Data Collection Instrument:**

- **Appendix A: Data collection form for demographic and contact information to be collected after initial consent prior to surgery**
- **Appendix B: Data form for day of surgery data collection**
- **Appendix C: The home diary to be completed by the subject**

• **Other Appendices**

- **Appendix D: Flow chart of recruitment to discharge**
- **Appendix E : Screening inclusion/exclusion**
- **Appendix F: Script for MSA's (Medical Support Assistants)**

IRBNet Number: 381600-19

PI: [name]

Protocol Title: **A randomized, single-blind, prospective trial of auricular acupuncture for the reduction of post-operative tonsillectomy pain in adults.**

Initial Date Submitted: 6/13/2013

Revision Date: 7/17/17

- **Appendix G: Optional Research Packet (flyer/information sheet/envelope)**
- **Appendix H: Data Excel**

• **Variables/Data Points:**

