## **7.3 DESIGN:**

- **Design type: Prospective, randomized control trial**
- **Sample**
  - **Description of the population:** All adults (>18 years) undergoing a tonsillectomy with or without adenoidectomy at WAMC are eligible for participation in the study.
  - **Sample Size: 125 subjects.** A target of 45 subjects per group for a total of 90 subjects, and accounting for a 10% drop out rate. With current diary return low, to ensure complete data for analysis we will continue to recruit and enroll up to 125 subjects.
  - **Power Analysis:** Under the assumption of a linear time by treatment interaction, assuming subject-level randomization, five time-points, power of 80%, a Type I error rate of 5% and no attrition, to detect a 1.6 difference in pain score requires a total sample size of 90 subjects or 45 per treatment arm.
  - **Inclusion Criteria:**
    - All adults (males and females) 18 yrs of age or older having a tonsillectomy or tonsillectomy with adenoidectomy.
    - ASA I-III
  - **Exclusion Criteria:**
    - Chronic pain syndromes (pain symptoms lasting greater than three months or taking opioids on a daily basis for > 3 months)
    - ASA IV

IRBNet Number: 381600-19

PI: [name]

Protocol Title: **A randomized, single-blind, prospective trial of auricular acupuncture for the reduction of post-operative tonsillectomy pain in adults.**

Initial Date Submitted: 6/13/2013

Revision Date: 7/17/17

- Prior neck or throat surgery
- Allergy to gold

- **Number of Participants:** Up to 125 subjects will be enrolled with a target of 90 subjects (45 per group) that have completed the study. .

- **Explanation of the process from consenting to data collection:**

- **Randomization:** Before the study begins, a randomized, sequential set of 100 numbered opaque envelopes will be prepared containing assignment to either the acupuncture group or the control group. The randomization list will be generated by a computer program. The envelopes will be stored in the PIs office and opened according to subject number on the day of surgery. To continue enrollment up to 125 another 25 will be randomized using a computer randomization program.

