## **11.0 BUDGET:**

**Will any outside organization provide funding or other resources?**

Yes

No

The funding for this study has ended. The PI chooses to continue enrollment for a larger pool for analysis.

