**iii. Is obtaining patient Authorization “impracticable”?**

- Yes – Authorization may qualify to be waived by the IRB. Please contact [[contact]](mailto:[contact]) for instructions.
- No – Research subjects will need to sign a HIPAA Authorization.

**iv. What precautions will you take to protect the confidentiality of research source documents (Case Report Forms, questionnaires, etc.), the research data file, and the master code (if any)?**

- All the enrolled subjects will be assigned a study identification number which will not be linked to any Identifiable Protected Health Information (PHI). There will be a master list linking the subject, including the subject's social security number, with the study ID which is kept in a password protected file on the V: drive . The subject's Social Security or other PHI will not be included in the study database. The master list will be destroyed after the study has been completed and all the data has been analyzed.
- Deidentified database without links to subject identifiers in an Excel spreadsheet will be stored on the WAMC V: drive. The deidentified data will only be shared among the PI, AI and collaborators of this study.
- The pain diary along with other case report forms will only be marked with the study ID and will be kept in a locked file cabinet in the research coordinator's locked office.

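### The day-of-surgery text lets the acupuncturist open the allocation envelope before meeting the awake subject and confirming enrollment, although the arm is not needed until after anesthesia

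*Combined protocol and SAP*

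**What the plan says.** Three places in section 7.3 bear on when the arm becomes known.

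- **Randomization bullet.** "The envelopes will be stored in the PIs office and opened according to subject number on the day of surgery". This sets the day and the matching number, and nothing else about timing.
- **Day-of-surgery paragraph.** It first states that "the randomization category will be determined by the PI or AI acupuncturists by opening the corresponding subject number envelope". Its next sentence reads "Prior to surgery, the PI or AI acupuncturists will introduce him or herself to the subject (if not already done so) and confirm enrollment", and the paragraph then moves on to anesthesia.
- **Needle-placement text.** "After the patient has been fully anesthetized, and prior to the start of the tonsillectomy, the study PI or AI acupuncturists will place" the needles in subjects assigned to acupuncture; controls receive nothing. The same text adds that "Initiation of the surgical case will not be delayed for acupuncture needle placement".

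Section 12.0, item iv, says "All the enrolled subjects will be assigned a study identification number". The title calls the trial single-blind. Section 7.0 makes the outcome a pain score reported by the subject on a 0 to 10 scale.

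**The concern.** There is no sham procedure. The subject's blinding rests on the needles going in under anesthesia and coming out before full awakening. A conversation just before anesthesia with the one person who knows the assignment is therefore a possible leak, through manner or words, in a trial whose outcome is what the subject reports.

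The second risk is to the enrollment check. If the person confirming enrollment already knows the arm, that knowledge could influence whether the subject goes forward. Such a loss might not be visible in the results. Section 7.3 aims for 90 subjects who complete the study, section 8.0 defines no analysis population, and the supplied text does not say what happens to a subject whose envelope is opened but whose enrollment is not then confirmed.

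Both risks are avoidable if nothing before needle placement depends on the arm.

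**Working it through.** No figure in the plan bears on this point, so the check compares the text on timing.

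**1. Events.** O = envelope opened; C = acupuncturist meets the awake subject and confirms enrollment; A = anesthesia; P = needles placed, or nothing done in a control.

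**2. Constraints in the text.**
- C comes before A: the day-of-surgery paragraph has anesthesia follow the contact.
- A comes before P: needles go in only under full anesthesia.
- O comes before P: the arm must be known by then.
- O falls on the day of surgery (Randomization bullet and day-of-surgery paragraph). Nothing relates O to C or A.

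**3. Orders that satisfy all of these.** C, A and P are fixed in sequence, and O can take any place before P. That gives three orders:
- O, C, A, P: the arm is known during the awake contact.
- C, O, A, P: the arm is not known during it.
- C, A, O, P: the arm is not known during it.

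One of the three permitted orders exposes the contact, and it is the order in which the sentences are written. This counts what the text allows. It does not estimate how often each order occurred.

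**4. Is the arm needed before P?** Anesthesia and pain medication follow standard of care under the assigned anesthesiologist, and controls have no intervention. No step described before P uses the arm. Either of the other two orders therefore loses nothing that the plan relies on.

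**5. Could the envelope be opened before consent?** In section 7.3, consent, the interview, the eligibility decision and the enrollment log come before the day-of-surgery step. Section 12.0 gives study numbers to enrolled subjects. Assuming that the envelope's subject number is this study number, the envelope belongs to someone who has already consented. Consent may be taken in holding on the day itself, so the steps can fall close together, but consent still comes first. The point therefore concerns only the contact before anesthesia and the final confirmation.

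**6. Reach.** A change affects only subjects not yet treated. The ceiling is 125, and section 11.0 says "The PI chooses to continue enrollment for a larger pool for analysis". No accrual count is given. The revision is dated 7/17/17 and section 5.0 expects data collection to end in July 2017, so the remaining number may be small.

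**The case against.** The strongest reply is that no sequence is prescribed. One sentence is tied to the day of surgery and the next to the time before surgery; the only sequencing word applies to anesthesia. A site that meets the subject first already complies. This stands: the text leaves a gap, and nothing shows that the unfavorable order was used.

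The enrollment check also leaves little stated room for discretion. Eligibility has been decided by then, and no criterion for dropping a subject at this step is given. This weakens the second risk but does not remove it, because the text still asks for a confirmation and lets it be made with the arm known.

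A reader might infer more than the documents support:

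- *That this is the acupuncturist's last contact with the awake subject.* The PI and AIs also collect data on the day of surgery, so later contact is not excluded. Only contact before anesthesia is supported.
- *That the order of events was never recorded.* The Figure 2 table has no entry for envelope opening, but it is a list of variables, not a form or log. It does not list the assigned group or the consent date either, and it names operating-room time twice. Appendix B (day-of-surgery form), Appendix D (flow chart) and Appendix H (data sheet) were not supplied, so the table says little about what is recorded.
- *That the added assignments are unconcealed.* The text says "To continue enrollment up to 125 another 25 will be randomized using a computer randomization program" and does not mention envelopes for them, but the day-of-surgery rule may already cover them. That is a separate clarification and not part of this point.

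It is also fair to object to delaying the opening until the subject is anesthetized. That adds no protection for the awake contact and could press against the rule that surgery must not wait. The fix does not require it.

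**Conclusion.** The point holds as a low-cost improvement. The written procedure permits the acupuncturist to know the arm while meeting the awake subject and confirming enrollment, and the plan gains nothing from that order. It does not require that order, and the documents do not show that allocation was opened before consent or that any subject was cued or dropped.

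The size of any bias is unknown; the documents supply no input for estimating it, and none is claimed. The conclusion assumes that the envelope's subject number is the study number given at enrollment, and that the appendices not supplied do not already set the order. If they do, the day-of-surgery paragraph only needs to be brought into line with them.

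**What to change.** For subjects not yet treated, reorder the day-of-surgery paragraph in section 7.3:

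1. The PI or AI acupuncturist meets the subject and confirms enrollment.
2. The envelope is opened only when that pre-anesthesia contact is finished, and before the needle-placement step, with needles ready so that surgery is not delayed.
3. The time of opening is entered on the Appendix B form, if it is not already there, and the Appendix D flow chart is made to match.

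The cost is reordered wording, perhaps one form entry, and the addendum that section 3.0, item J, already requires before a change. The practical burden is that the acupuncturist and the envelope, which is stored in the PI's office, must be available near the operating room in control cases as well.

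The change does not deal with knowledge of the arm during later contact or data collection, and it cannot help subjects already treated.

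### PACU pain scores in the primary outcome may be recorded by the anesthesiologist, who very likely knows the arm, and no masking is stated for phoned diary scores or opioid conversion

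*Combined protocol and SAP*

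**What the plan says.** The title calls the study "A randomized, single-blind, prospective trial of auricular acupuncture for the reduction of post-operative tonsillectomy pain in adults", but no section says who is blinded, and no assessor, data collector or analyst is described as masked.

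**Who learns the arm (section 7.3, day of surgery).** "the randomization category will be determined by the PI or AI acupuncturists by opening the corresponding subject number envelope". On placement of the needles: "After the patient has been fully anesthetized, and prior to the start of the tonsillectomy, the study PI or AI acupuncturists will place the acupuncture". They stay in until the end of the case and are removed by the PI or a designee before the patient is fully awake. For controls, "If the patient is randomized to the control group, no intervention will occur". No sham, drape or screen is described.

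**Who records pain in the PACU (same section).** "the providing anesthesiologist or PACU nurse will document in Essentris" a score four times in the first hour and hourly after that. The mixed-model row of Figure 3 starts immediately after surgery, and the Sum of Pain Intensity (SPI) in section 7.2 starts at first waking. PACU scores therefore fall in the primary outcome under either description.

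**Who handles the other data (section 7.3).**
- Day of surgery: "Data will be collected by the PI, AIs, on the day of surgery and recorded on the form found in Appendix B". Essentris or the anesthesia record may also be used as the source.
- Home diary: "Subjects will be asked to return their pain scores by phone, email, or mail (addressed envelope provided"). The person who takes a phoned score is not named.
- Opioid totals "will be converted to IV morphine equivalents by the PI or research staff member".

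**The concern.** Pain on the 0 to 10 scale is the patient's own report, but in the PACU a second person asks for it, interprets a drowsy answer and writes down a whole number. If that person has just managed a patient with needles in both ears, or one without, knowledge of the arm can affect the prompt and the recorded value. The same applies, less strongly, to a diary read out over the phone. It applies more weakly still to converting doses to morphine equivalents, which feeds the home-medication comparison in Figure 3.

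This is separate from allocation concealment. Perfectly concealed envelopes would still leave a recorder who knows the arm. At stake are the early pain difference and the rate of change in pain, which section 8.0 names as a target of the mixed model. A favourable early result would be open to an observer-bias objection that the plan gives no means of answering.

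**Working it through.** **1. The plan's only nearby figure.** Section 7.3 gives 45 per arm for a 1.6-point difference, 80% power and 5% type I error. No SD, within-subject correlation or sidedness is stated, so the figure cannot be reproduced. As a two-sided comparison of two means it implies SD = 1.6 / [(1.96 + 0.84) × √(2/45)] ≈ 2.71. That SD is used only in step 5.

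**2. Weight of the PACU scores.** Section 7.3 schedules at least 4 scores in the first PACU hour, 4 six-hourly home scores and about 9 daily scores (days 2 to 10), so 17 in all. PACU share = 4/17 = 23.5%. With 12 to 14 home scores the share is 25% to 22%.

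**3. Effect on the unweighted mean.** Assume a shift of 0.5 to 1.0 point in every PACU score of one arm. The documents give no such figure.
- 0.5 × 4/17 = 0.12; 1.0 × 4/17 = 0.24 (0.235 before rounding).
- Against 1.6: 0.118/1.6 = 7%; 0.235/1.6 = 15%.
- If nurses record half of the scores: 0.06 to 0.12 point.

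**4. Effect on a straight line in time.** Assumed times: PACU at 15, 30, 45 and 60 minutes; home at 8, 14, 20 and 26 hours; then days 2 to 10. In days:
- Sum of times = 0.104 + 2.833 + 54 = 56.94; mean = 56.94/17 = 3.349; sum of squares about the mean = 195.6.
- Slope change per point of shift = (0.104 − 4 × 3.349)/195.6 = −0.068 per day. For 0.5 to 1.0 point this is 0.034 to 0.068 per day, or 0.34 to 0.68 over ten days (21% to 42% of 1.6).
- Time-zero change per point of shift = 4/17 + 0.068 × 3.349 = 0.46. For 0.5 to 1.0 point this is 0.23 to 0.46.
- Leverage of one PACU score = 1/17 + (3.349 − 0.026)²/195.6 = 0.115. The average is 2/17 = 0.118. For day 10 it is 1/17 + (10 − 3.349)²/195.6 = 0.285.

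If PACU scores are shifted down in the acupuncture arm, the fitted lines show a spurious early benefit that wanes.

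**5. False-positive rate for the mean.** Take SD 2.71 as the SD of each patient's mean score (an assumption). Standard error = 2.71 × √(2/45) = 0.571. With shift b, the rate is Φ(b/0.571 − 1.96) + Φ(−b/0.571 − 1.96). For b = 0.12 this is 5.5%; for b = 0.24 it is 7.0%. With SD 2.0 the rates are about 6% and 9%.

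**6. Time-weighted SPI.** By the trapezoid rule, a unit PACU shift contributes 0.75 h, plus half of the 7 h to the first home score, so 4.25 h out of 239.75 h = 0.018. A shift of 0.5 to 1.0 moves the time-weighted mean by only 0.01 to 0.02 point. The protocol specifies no weighting.

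**The case against.** The case against is substantial, and much of it stands.

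- **A reader might infer that the outcome steps fall to the acupuncturist.** The text does not say so. Conversion is by the PI or a research staff member using a fixed published converter, data entry is by a research team member, and nobody is named for phone intake. Day-of-surgery collection is largely transcription, since Essentris is the source for PACU scores and can be audited. What stands is that masking is stated for none of these steps.
- **A reader might infer that PACU scores have strong leverage on the slope, or that the time-zero difference takes the full shift.** Step 4 shows otherwise. Each PACU score has about average leverage, and the fitted time-zero difference moves by 0.46 of the shift. The full shift would appear only in a PACU-only comparison, which Figure 3 does not list.
- **The size is a worst case.** It needs every PACU score in one arm to shift, while section 7.3 also names the PACU nurse and gives no split. Section 8.0 speaks of daily scores and the power analysis of five time-points, so the weight of PACU scores is itself unsettled.
- **The anesthesiologist's knowledge is inferred.** No sentence says that this person watches the needles. The inference is strong because the needles stay in the ears throughout the case.
- **Most scores are better protected.** About 13 of 17 come from the subject's own diary, and the patient is anesthetized for placement and not fully awake at removal.
- **Little time remains.** The revision is dated 7/17/17 and section 5.0 expected data collection to end that month. Section 11.0 says enrollment continues, however, and records not yet processed can still be handled by masked staff.

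**Conclusion.** The concern holds as a modest, avoidable bias route. The plan lets a person who very likely knows the arm document scores that enter the primary outcome, and it states no masking for phoned diary scores or opioid conversion. In the worst case, on an assumed 0.5 to 1.0 point shift, the bias is 0.12 to 0.24 point in an unweighted mean. In a straight-line fit it is 0.23 to 0.46 point at time zero and 0.03 to 0.07 point per day in slope. It falls in proportion to the share of scores recorded by nurses and nearly vanishes in a time-weighted SPI.

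The documents do not show that any such shift occurred, or that one person controls the outcome data. The point is worth acting on because the remedy is cheap. It does not by itself invalidate the primary comparison.

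**What to change.** 1. **PACU scores.** For subjects still to be enrolled, define study PACU scores as those the PACU nurse documents in standard care. Flag any score recorded by the anesthesiologist, leave it out of the primary analysis and include it in a sensitivity analysis.
2. **Handling of data.** Assign phoned diary intake, extraction of PACU scores from Essentris and the morphine conversion to an existing research team member who has not seen the allocation. Complete these steps before the arm code is merged. Needle type and retention time, which Figure 2 has the PI document, reveal the arm and should be kept from that person until then.
3. **Blinding statement.** Say in section 7.3 who is blinded and who is not.

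**Cost.** Protocol wording and a division of tasks among existing staff. Nurses do nothing new, since the rule only selects among scores already taken in routine care. This matters because section 14.0 marks nursing involvement as not required. The rule needs the source entry to show who recorded each score; if it does not, that has to be noted at collection. The downside is a few missing early scores. The mixed model can accommodate these if their absence is unrelated to the unrecorded pain level, and the sensitivity analysis shows whether they matter. No change to ear preparation, the clinical handover or the clinical note is proposed: the first would add a procedure, and the other two touch clinical communication.
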